7.5 Medical Monitoring

It is the responsibility of the Principal Investigator to oversee the safety of the study at his/her site. This safety monitoring will include careful assessment and appropriate reporting of adverse events as noted above, as well as the construction and implementation of a site data and safety-monitoring plan (see section 10 Auditing, Monitoring and Inspecting). Medical monitoring will include a regular assessment of the number and type of serious adverse events.

7.5.1 Internal Data and Safety Monitoring Board

Adverse Events and Serious Adverse Events will be assessed and recorded with oversight by an institutional DSMC (Data Safety and Monitoring committee) that will meet after the 7th patient has completed the study. At that point, the Data and Safety Monitoring Committee (DSMC) will meet to determine whether enrollment may continue to the randomized portion of the study.

In compliance with the Washington University Institutional Data and Safety Monitoring Plan, the DSMC will meet to review toxicity data at least every 6 months. The report will be prepared by the statistician with assistance from the study team and will be submitted to the Quality Assurance and Safety Monitoring Committee (QASMC). This report will include:

- HRPO protocol number, protocol title, Principal Investigator name, data coordinator name, regulatory coordinator name, and statistician
- Date of initial HRPO approval, date of most recent consent HRPO approval/revision, date of HRPO expiration, date of most recent QA audit, study status, and phase of study
- History of study including summary of substantive amendments; summary of accrual suspensions including start/stop dates and reason; and summary of protocol exceptions, error, or breach of confidentiality including start/stop dates and reason
- Study-wide target accrual and study-wide actual accrual
- Protocol activation date
- Average rate of accrual observed in year 1, year 2, and subsequent years
- Expected accrual end date and accrual by arm
- Objectives of protocol with supporting data and list the number of participants who have met each objective
- Measures of efficacy
- Early stopping rules with supporting data and list the number of participants who have met the early stopping rules
- Summary of toxicities separated by arm
- Abstract submissions/publications
- Summary of any recent literature that may affect the safety or ethics of the study

The study principal investigator and Research Patient Coordinator will monitor for serious toxicities on an ongoing basis. Once the principal investigator or the Research Patient Coordinator becomes aware of an adverse event, the AE will be reported to the HRPO and QASMC according to institutional guidelines.

Additionally, if two or more serious adverse events of a similar nature occur and a causal relationship to the investigational product cannot be excluded, accrual to the randomized portion will not occur.

A DSMC will consist of no fewer than 3 members including 2 clinical investigators and a biostatistician. Like investigators, DSMC members are subject to the Washington University School of Medicine policies regarding standards of conduct. Individuals invited to serve on the DSMC will disclose any potential conflicts of interest to the trial principal investigator and/or appropriate university officials, in accordance with institution policies. Potential conflicts that develop during a trial or a member's tenure on a DSMC must also be disclosed.

Refer to the Washington University Quality Assurance and Data Safety Monitoring Committee Policies and Procedures for full details on the responsibilities of the DSMC at https://siteman.wustl.edu/research/clinical-research-resources/

8 Data Handling and Record Keeping

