2.1 General Design

Figure 1. Trial schema

Type of Study: Open-label clinical trial where all patients receive TUDCA at 1.75 or 2g/day for 6 weeks, divided into three doses, after meals.

Schematic of Trial Design: A total of 12 individuals with active ulcerative colitis and endoscopic evidence of inflammation will be eligible to participate in this open-label clinical trial using TUDCA (adjunct or primary therapy) at 1.75 or 2g/day for 6 weeks, divided into three doses, after meals as summarized in Figure 1. A full schedule of visit assessments and procedures is defined in Table 1 in Section 5.

Duration of Subject Participation: 6 weeks on Trial + 2 weeks Follow up = 8 weeks.

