3.3 Subject Recruitment and Screening

Recruitment: Division of Gastroenterology at Washington University: More than 2500 patients with IBD annually are cared for by the Division's IBD specializing gastroenterologists (n=10). The division actively participates in IBD clinical trials (8 in 2016 alone) and has an established infrastructure for recruitment and execution of new studies examining IBD specific medications. As a leading center for IBD patients sample Biobanking, the Washington University IBD Division also has a robust infrastructure for acquiring and rapidly processing research quality IBD specimens including serum samples, stool and biopsy material. Two of the Washington University site PIs (Drs. [name] and [name]) have worked in the field of IBD for more than 10 years. We anticipate enrolling 2-3 patients per month.

Screening:

Medical examination. All subjects will be screened with a detailed history and physical examination, pregnancy test (*if female*) and laboratories including CBC, complete metabolic panel with a liver panel, C-reactive protein and fecal calprotectin.³¹

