4.3 Method for Assigning Subjects to Treatment Groups

Open label study. All patients will receive TUDCA.

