6.1 Sample Size Determination for Primary Endpoint

Estimates of change in the primary outcomes: We expect that TUDCA treatment will lead to similar changes on ER stress markers in UC patients as that in IBD mouse models. As judged by quantification results of western blot, the expression levels of ER stress markers in IBD mouse models were significantly reduced by 25% to 45% after TUDCA treatment.⁴ A previous publication, as well as our own data, has shown that standard deviations of the ER stress markers are less than ½ of the means in intestinal biopsy samples of IBD patients⁴⁰. Considering there might be greater variation after the TUDCA treatment, we set the standard deviations at half of the means of all the ER stress markers (Table 2).

Table 2 Sample size calculation

ER stress markers	Difference between means	Estimated standard deviation	Sample size at power=0.8	Sample size at power=0.9
p-elF2α	1.16-0.64=0.52	0.26	5.09	6.39
XBP1s	1.21-0.73=0.48	0.24	5.09	6.39
BIP	1.13-0.84=0.30	0.15	5.09	6.39

Power Estimates for each primary endpoint: We used the quantification results of western blot on ER stress markers to calculate the sample size needed. Since the impact of TUDCA on intestine tissues in humans has not been examined, we used the difference between the mean values of ER stress markers in groups treated with or without TUDCA that we obtained in murine studies.⁴ Power analysis using the R software shows that 7 patients are sufficient to detect the difference before and after the treatment, when P<0.05 is considered significant. Due to the relatively variability in IBD patient disease activity and high dropout rate in IBD clinical trials, we will enroll a total of 12 patients will be recruited for the study with an expected

Statistical analysis: We will be specifically interested in the statistical contrasts that compare before and after TUDCA treatment. Correlation between the primary end point and secondary end point will also be examined. The appropriateness of all analysis of variance and covariance models will be evaluated using regression residuals. If normality or homoscedasticity requirements are violated, data transformations will be explored and, if appropriate transformations cannot be found, analyses may be done semi-parametrically using the ranks of the data.

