7.4 Stopping Rules

Individual stoppage criteria-

Based on extensive clinical trial data, we anticipate that TUDCA will be well tolerated. However, patients will be monitored via study visits and phone calls and will permanently discontinue study drug for any adverse event possibly or probably related to study drug that is considered of *moderate or severe intensity*. To define intensity, we will utilize a standard severity rating scale to ensure this safety monitoring plan is enforced in a standardized fashion. Individual subjects should be discontinued for any adverse event rated a Grade 3 or greater in severity on the Common Terminology Criteria for Adverse Events (CTCAE_v5.0 November 2017) scale v, unless it is clearly related to the underlying disease.

For disease specific symptoms (e.g. diarrhea, rectal bleeding) we will consider disease worsening as an increase in >3 points on the Mayo Score to be potentially related to TUDCA and will lower the dose to 1000 mg as described. If symptoms persist or worsen over the subsequent 5 days, the patient will be permanently discontinued from the study.

Study stoppage criteria-

Enrollment of new subjects should be interrupted should 2 or more patients experience CTCAE Grade 3 event, or 1 or more patients experience CTCAE Grade 4 events not clearly related to the underlying disease. Study enrollment may be resumed following review of all available safety data by the investigator and study team and a concurrent opinion that the totality of the data suggests this event is unlikely to be related to TUDCA. The study should be terminated if, following the review of the safety data, it has not been possible to demonstrate that the adverse event has a clear relationship to the underlying disease or associated co-morbidity.

We will initiate early study termination or enroll all future patients at the 1000 mg dose. This decision will be made with the guidance of the appointed Data Safety and Monitoring Committee. Individual and study stoppage criteria should be applied to these patients as well.

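### The DSMC decision on continuing enrollment waits for the 7th completer, when 10-12 of the 12 patients would already be enrolled (9-11 if completion means week 6), and it refers to a randomized portion that does not exist

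*Combined protocol and SAP*

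**What the plan says.** Section 7.5.1 places adverse-event oversight with an institutional DSMC "that will meet after the 7th patient has completed the study". At that point the committee "will meet to determine whether enrollment may continue to the randomized portion of the study". The same section adds that "the DSMC will meet to review toxicity data at least every 6 months".

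The design has no randomized portion. Section 4.3 reads "Open label study. All patients will receive TUDCA", and section 6.1 says "we will enroll a total of 12 patients". On pace, section 3.3 states "We anticipate enrolling 2-3 patients per month", and section 2.1 gives the length of participation as "6 weeks on Trial + 2 weeks Follow up = 8 weeks". No section holds enrollment while the first seven patients complete.

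Other controls are driven by events or run by the study team:
- Section 7.4: "Enrollment of new subjects should be interrupted should 2 or more patients experience CTCAE Grade 3 event", or after one Grade 4 event, when not clearly due to the underlying disease. The investigator and study team review the data before enrollment resumes.
- Section 6.2: a trigger when at least half of patients have a TUDCA-associated side effect or intolerance, acted on with DSMC guidance. It has no minimum grade and no stated time of evaluation.
- Section 7.5.1: ongoing toxicity monitoring by the investigator and coordinator, with adverse events reported to HRPO and QASMC.
- Section 9.1: weekly team review, and a study stop for a serious adverse event that raises risk to participants.

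**The concern.** A review that decides on further enrollment is useful to the extent that patients remain to be enrolled. Here the trigger is a completed patient, participation takes two months, and accrual carries on meanwhile. In a trial of 12, most or all of the last five patients can enter while the 7th is finishing.

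The wording adds a second problem. Read literally, the decision concerns a stage that the protocol does not contain, so the text does not say that the review governs patients 8-12. The same phrase limits another safeguard in 7.5.1: two or more similar serious adverse events for which a causal link cannot be excluded block accrual only to that non-existent portion.

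What is at stake is independent review of tolerability below the level of severe events. Section 1.4 calls this the first TUDCA trial in ulcerative colitis, and section 6.2 says that the drug has not been examined specifically in this population and may worsen diarrhea.

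**Working it through.** The documents give no figure for the number enrolled at the review, so there is none to reproduce. It follows from their own inputs.

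**Inputs.** Total 12 (6.1). Accrual r = 2 to 3 per month (3.3), with 2.5 as midpoint. Time from start of treatment to completion w = 8 weeks (2.1), or 6 weeks if completion means the final visit in Table 1. One month = 365.25/12/7 = 4.348 weeks. Assumptions: even accrual, enrollment counted at start of treatment, the first seven enrolled all complete, and no pause.

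**Enrolled when the 7th completes** = 7 + r × w/4.348, rounded down to whole patients and capped at 12.

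| r per month | w = 8 weeks | w = 6 weeks |
|---|---|---|
| 2 | 7 + 3.68 = 10.68, so 10 | 7 + 2.76 = 9.76, so 9 |
| 2.5 | 7 + 4.60 = 11.60, so 11 | 7 + 3.45 = 10.45, so 10 |
| 3 | 7 + 5.52 = 12.52, so 12 | 7 + 4.14 = 11.14, so 11 |

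Patients not yet enrolled: 2, 1 and 0 at 8 weeks; 3, 2 and 1 at 6 weeks. At 3 per month and 8 weeks, the 12th patient enters at 11/3 × 4.348 = week 15.9 and the 7th completes at 6/3 × 4.348 + 8 = week 16.7, so enrollment has already closed.

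**Still on drug or not yet enrolled**, with 6 weeks on drug and the review at the 7th patient's week 8. At 2 per month, patients 8-10 are on drug and 11-12 unenrolled: 5. At 2.5 per month, 9-11 are on drug and 12 is unenrolled: 4. At 3 per month, 9-12 are on drug: 4. With the review at week 6 it is all of patients 8-12: 5.

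**The 6-monthly meeting.** The 12th patient enters 11/r months after the first: 11/3 = 3.7 to 11/2 = 5.5 months. A first meeting 6 months after the first patient would come after that.

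**Sensitivity.** If one early patient withdraws, so that the 7th completer is the 8th enrolled, the range over both definitions is 10-12. A 4-week month also gives 10-12. With random (Poisson) accrual, the chance that at least 9 are enrolled at the review is about 76% at the slowest setting (2 per month, 6 weeks) and 97% at the fastest (3 per month, 8 weeks).

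**An earlier look.** At the 3rd week-6 completer, enrolled = 3 + r × 6/4.348 = 5.76, 6.45 and 7.14, so 5, 6 or 7, with 7, 6 or 5 still to enroll.

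**The case against.** Four points can be made in the plan's defense.

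1. *The review may not be meant to gate patients 8-12.* The text speaks of a randomized portion, and if a later randomized stage were planned, a review after 7 of 12 open-label patients would precede it. The wording could also imply a hold at seven. Neither reading is supported: the protocol describes no such stage and states no hold. Within this protocol, the rest of the 12 are the only enrollment that the review can govern. It does stand that the wording needs reconciling.

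2. *The review still helps patients on treatment.* This stands. A reader might infer that almost nobody is left to protect; the count of 4-5 on drug or unenrolled shows otherwise. Those counted as enrolled are also not all on study, since seven have completed.

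3. *Other safeguards act earlier.* This stands and limits the consequence. In particular, the section 6.2 trigger has no minimum grade and needs no scheduled meeting, and HRPO and QASMC lie outside the study team. It would be wrong to infer that tolerability goes unwatched. What is missing is a scheduled independent review of the cumulative data early enough to bear on enrollment.

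4. *The 6-monthly meeting could come in time.* It is a minimum frequency with no stated start. Counted from activation, at 2 per month, a first patient more than about two weeks later (6 - 5.5 = 0.5 month) would put the meeting before the 12th enrollment. So the documents do not show that the meeting falls too late, only that nothing requires it to fall in time.

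**Conclusion.** The point holds as a matter of timing and wording. Followed as written, the only scheduled DSMC decision on enrollment comes with 10-12 of 12 patients enrolled (9-11 if completion means week 6) and can affect 0-3 new patients. It does not follow that the review is worthless or that earlier protection is absent.

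The size rests on even accrual at a rate that is only anticipated, on enrollment being counted from the start of treatment, and on the absence of a stated pause. Slower accrual would leave more patients to enroll after the review; early withdrawals would leave fewer, and section 6.1 itself expects high dropout. This should be changed: the gain is specific and the cost small, while the event-driven rules keep it from being more serious.

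**What to change.** In section 7.5.1:

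- Replace the references to a randomized portion with a statement that the review governs enrollment of the remaining patients of the 12, and reconcile the rule on similar serious adverse events with the single-arm design in the same way. State whether completion means week 6 or week 8.
- Add one DSMC review while about half the patients remain to be enrolled. The 3rd week-6 completer is one example, not a derived optimum.
- Keep the 7th-completer review, because the earlier look carries less information. For an event with an assumed true rate of 20%, three completers show at least one with probability 1 - 0.8^3 = 49%, against 1 - 0.8^7 = 79% for seven.

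The cost is one extra DSMC meeting on data already being collected, with no added patients or procedures.

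Alternatively, if the 7th-completer review stays the only gate, state that no 8th patient is enrolled until the DSMC has met. That costs a pause of about 6-8 weeks of accrual plus the time to convene the meeting.

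### Both accrual safeguards in section 7.5.1 act on a randomized portion that this single-arm study does not have

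*Combined protocol and SAP*

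**What the plan says.** Section 4.3 gives the allocation: "Open label study. All patients will receive TUDCA". Section 2.1 and the study summary describe 12 patients on one open-label treatment. No section describes randomization.

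Section 7.5.1 contains two provisions on accrual:

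- An institutional DSMC "that will meet after the 7th patient has completed the study", and its task at that point is to "determine whether enrollment may continue to the randomized portion of the study".
- If two or more similar serious adverse events (SAEs) occur and "a causal relationship to the investigational product cannot be excluded, accrual to the randomized portion will not occur".

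The same section adds that "the DSMC will meet to review toxicity data at least every 6 months". It also asks for accrual and toxicities to be reported by arm.

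Study-level rules appear in three other places:

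- **Section 7.4:** "Enrollment of new subjects should be interrupted should 2 or more patients experience CTCAE Grade 3 event", or 1 or more patients a Grade 4 event, not clearly related to the underlying disease. The investigator and study team may resume enrolment after a safety review. A last paragraph provides for termination or enrolment at 1000 mg, with DSMC guidance, but gives no condition.
- **Section 6.2:** gives that condition (at least 50% of patients with a TUDCA-associated side effect or intolerance) and refers to 7.4 for the full rules.
- **Section 9.1:** stops the study after an SAE that increases risk to participants, with a findings report before it resumes.

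**The concern.** A stopping rule must act on something that happens in the trial. Both accrual provisions in 7.5.1 act on a stage that never occurs. If two similar, possibly drug-related SAEs were seen, the rule would withhold accrual that nobody had planned and would leave open-label enrolment untouched. The DSMC meeting after patient 7 would be asked about a continuation that does not exist. The request for data by arm suggests that the text was carried over from another design, but that is an inference.

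What is at stake is clarity in a safety rule. Section 1.4 describes this as the first trial of TUDCA in ulcerative colitis, so the team and the DSMC should be able to read from the protocol what is halted, and when.

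**Working it through.** The documents give no operating characteristic for any stopping rule and no SAE rate. There is no figure to reproduce, and no event probability is claimed here. The main check sets the sections side by side.

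**1. Literal effect of 7.5.1.** By 2.1 and 4.3, the number of patients in a randomized portion is 0. A bar on accrual to it therefore removes 0 of the 12 patients, however many SAEs occur. The same holds for the accrual decision after patient 7.

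**2. Do other rules cover the same ground?**

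- *7.4 has a different trigger.* It counts patients by CTCAE grade. Section 7.1 defines seriousness by outcome (including an important medical event) and not by grade. Two similar SAEs graded below 3, or two Grade 3 SAEs in the same patient, need not meet the 7.4 trigger.
- *7.4 has a different consequence.* Where both apply, 7.4 interrupts enrolment and lets the investigator and study team resume it. The wording in 7.5.1 is a bar.
- *9.1 is broader but rests on judgement.* It applies to an SAE that increases risk. It states no count and no DSMC role.
- *6.2 and the end of 7.4* give the DSMC a say on termination or the 1000 mg dose, under the 50% condition.

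The overlap is substantial but incomplete.

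**3. Wording of 7.4.** The individual rule covers Grade 3 or greater. The study-level rule names Grade 3 and Grade 4 and stops there, so a fatal event is not literally a trigger. The 50% condition is missing from 7.4 but present in 6.2.

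**4. Timing of the patient-7 review (a separate point).** Inputs: "We anticipate enrolling 2-3 patients per month" (3.3) and "6 weeks on Trial + 2 weeks Follow up = 8 weeks" (2.1). Assumptions: first dose of patient 1 at month 0, even spacing at r per month, no dropout, no enrolment pause. With 30.44 days per month, 6 weeks is 42/30.44 = 1.38 months and 8 weeks is 56/30.44 = 1.84 months; call this f.

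Patient 7 enters at 6/r and completes at 6/r + f. Enrolled by then = 1 + floor(r × (6/r + f)) = 7 + floor(r × f), capped at 12.

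| r per month | f (months) | r × f | Enrolled | Left |
|---|---|---|---|---|
| 2 | 1.38 | 2.76 | 9 | 3 |
| 2 | 1.84 | 3.68 | 10 | 2 |
| 3 | 1.38 | 4.14 | 11 | 1 |
| 3 | 1.84 | 5.52 | 12 | 0 |

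Variations:

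- *Slower accrual, 1 per month:* r × f is 1.38 or 1.84, so 8 are enrolled and 4 are left.
- *Enrolment counted from consent, up to 2 weeks (0.46 months) before baseline:* with f + 0.46 in place of f, 0-2 are left.
- *Pause after patient 7:* 12 − 7 = 5 are left. Patient 8 then waits f instead of 1/r. In weeks, 1/r is 2.17 at 2 per month and 1.45 at 3 per month, so the delay runs from 6 − 2.17 = 3.8 to 8 − 1.45 = 6.5, about 4 to 6.5 weeks plus the meeting.
- *Review after the 4th completer, no pause:* enrolled = 4 + floor(r × f) = 6, 7, 8 or 9, leaving 3-6.

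**The case against.** The strongest defence is that the intent is obvious and other safeguards apply. Any reasonable team would read the phrase as the remaining patients. Section 7.4 permanently discontinues a patient for a possibly related event of moderate or severe intensity, so a second similar SAE in the same patient would usually fall off drug. Section 9.1 can stop the study for a single SAE, and the team reviews safety weekly. All of this stands, and it limits the consequence. It does not make the rule correct, because the protocol should not rely on readers to replace its words.

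Several stronger readings are tempting, but the documents do not support them:

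- *That the DSMC has no real decision to make.* Sections 6.2 and 7.4 give it a role in termination or dose reduction. Its report must cover the stopping rules, and its full responsibilities are deferred to an institutional policy that is not in the documents.
- *That a death would be ignored.* Section 9.1 provides a stop and immediate IRB reporting of a death. The missing Grade 5 is a wording slip of small weight.
- *That 7.4 and 9.1 contradict each other, or that the 50% rule is absent.* Both sections can be obeyed together, and the 50% rule is in 6.2. Having the rules spread over several sections is a matter of organisation.
- *That the patient-7 meeting is the only DSMC review during enrolment.* The start of the 6-month clock is not stated. At 2 per month the 12th patient enters at 11/2 = 5.5 months, so a clock that started more than about two weeks before the first patient would put a review inside enrolment.

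The timing result is also not a measure of the wording defect. It would be the same after correction, and it disappears if the provision on whether enrolment may continue is applied as a gate.

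**Conclusion.** Section 7.5.1 is wrong as written and should be corrected. Its consequence for repeated similar SAEs, and its accrual decision after patient 7, apply to 0 of the 12 patients. This follows from the text and needs no assumption about event rates. Because other safeguards overlap with much of the intended protection, the defect is an ineffective rule and not an unprotected trial. The two gaps in 7.4 are minor.

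Whether the patient-7 review comes late is a separate, optional point. The figure of 0-3 patients left depends on even spacing from first dose, no dropout, no pause and the planned 2-3 per month. At 1 per month 4 are left; with a pause, 5.

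**What to change.** **Section 7.5.1 (needed).**

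- In the sentence on repeated SAEs, state the consequence as: *further accrual to this study will not occur*. Keep it as a bar. Changing it to an interruption pending review would weaken the rule.
- In the sentence on the DSMC meeting, say that the committee decides whether enrolment may *continue beyond the patients already enrolled, up to 12*.

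**Section 7.4 (minor, same edit).**

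- Make the second study-level trigger *CTCAE Grade 4 or greater*.
- Repeat the 50% condition from 6.2 at the start of the last paragraph.
- Do not extend the 9.1 findings report to every resumption under 7.4. That would be a new requirement, because 7.4 can be triggered by non-serious events.

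These changes cost a wording amendment and its IRB submission. They add no patients and no procedures.

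**Optional, for the sponsor to choose.** State whether enrolment pauses for the patient-7 review. A pause keeps 5 patients subject to the decision, at about 4 to 6.5 weeks plus the meeting. Reviewing after the 4th completer without a pause would leave 3-6 patients and avoid that delay.
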